2.1.1.5 Study completion and last contact

A patient will be considered to have completed the study when the patient has completed the last visit planned in the protocol.

[figure not shown]
Study completion for a patient can occur after he/she has completed 52 weeks of treatment in Treatment Period 1, or after the additional 104 weeks of treatment in optional Treatment Period 2 (total of 156 weeks of treatment) or if they have prematurely withdrawn. Completion of the study will be when all randomized patients have met the definition of study completion described above and have completed the post-treatment follow-up visit.

For all patients/subjects a safety follow-up visit (visit 401) should be conducted (e.g. by telephone) 30 days after last visit (299, Week 52 for patients not continuing into Treatment Period 2 and visit 399, week 156 for patients completing Treatment Period 2).

The maximum of the date of last visit, date of last phase completion, date of withdrawal of consent would be the date of last contact for the patient participating in the study.

2.1.1.6 Data pooling and assessment windows

If a scheduled visit did not occur, the data from the treatment discontinuation or study discontinuation visit may be used as the data from the scheduled visit, if the treatment discontinuation or study discontinuation visit occurred closer to the planned study day of the missing scheduled visit than to the planned study day of any other scheduled visit. In this case the treatment discontinuation or study discontinuation visit will be treated as the scheduled visit for the purpose of all analyses. Otherwise the data from any scheduled visit that did not occur will be dealt with like any other missing data. If the treatment discontinuation or study discontinuation visit is not re-mapped to any scheduled visit, it will be treated as an unscheduled visit that does not appear in by-visit summaries.

Subgroup analyses contributing key regulatory information will be provided for each country or region in line with regulatory requirements.

Patients randomized to the study in the sites in China will be considered as the Chinese patients. Separate analyses on Chinese patients will be performed and the specific outputs will be marked by suffix 'C' in the study TFL shells. Patients randomized to the study in the sites in China, Japan, Taiwan, and Korea will be considered as Asian patients. Separate analyses on Asia region subgroup will be performed and the specific outputs will be marked by suffix 'AS' in the study TFL shells.

2.3 Patient disposition, demographics and other baseline characteristics

Patient demographics and baseline characteristics including age, sex, race, ethnicity, height, weight, body mass index (BMI), relevant medical history, smoking history, asthma duration, background therapies, pre- and post-bronchodilator FEV1, [REDACTED], percent predicted FEV1, [REDACTED], number of exacerbations in the previous year prior to screening will be summarized by treatment group for the SAF. Categorizations of age will include the categories of <18 years, >=18- <65 years and >=65 years of age. For rollover patients, summaries mentioning the number of patients who were adolescents (< 18 years age) at the start of the previous Phase 3 study but are adults (>= 18 years age) at the start of study A2315 will also be presented.

For rollover patients, relevant medical histories and adverse events that started and stopped in the prior phase 3 study will be recorded in Medical History CRF page of this study per investigator's judgement. Ongoing AEs in the prior phase 3 study will be recorded in Prior Study Adverse Event Outcome CRF page of this study and considered as medical history.

2.3.1 Patient disposition

The number of patients screened, randomized, completed and discontinued from the study (in overall treatment period, treatment period 1 and treatment period 2 separately) will be summarized on overall population and by source of patients (i.e., rollover patients from Study A2307/A2314, rollover patients from Study A2316/A2317, and new patients). In addition, a similar summary for overall population will be provided by country. Overall treatment period is defined as combined treatment period 1 and treatment period 2 (treatment period 1 only in the case of patients not continuing into treatment period 2). Patients discontinued from the study will be summarized with reasons for discontinuation. Rescreening information will also be summarized mentioning the number of patients who were rescreened and how many of them were randomized.

Time to study discontinuation will be displayed graphically for each treatment group by source of patients using a Kaplan-Meier curve for the FAS. The date of study discontinuation is defined as the maximum of the last known visit date in treatment period and the date of last dose of study medication. Patients who completed the study will be censored at the final visit.

Number of patients with protocol deviations and protocol deviations that lead to exclusion from analysis sets will be tabulated by deviation category and treatment group for the RAN.

The number of patients included in each analysis set will be tabulated by treatment group on overall population and by source of patients on the RAN. Reasons for exclusions from analysis sets will be tabulated. Patient exclusion from analysis sets will be listed for all patients with reasons for exclusion (including protocol deviations).

2.4 Treatments (study treatment, rescue medication, concomitant therapies, compliance)

2.4.1 Study treatment / compliance

The duration of exposure, the number of patients randomized who completed the foreseen course of study medication and the number of patients who discontinued from the study medication will be summarized on overall population, by source of patients, by source of patients and prior treatment in a prior Phase 3 study. Since the study has a double dummy design each patient will be dispensed two bottles of study medication at the dispensing visits. Bottle 1 has study medication corresponding to 150 mg QAW039 or placebo and Bottle 2 has study medication corresponding to 450 mg QAW039 or placebo. Exposure and compliance will be presented on the SAF. Exposure will be presented for each treatment while compliance will be presented by treatment arm for each of the bottles separately.

Duration of exposure to a treatment will be calculated as the number of days between the first dose date and the last dose date exposed to that treatment over the specified period (expressed as: Duration of exposure = Date of last known dose of study drug – Date of first dose of study drug + 1). In addition, the duration of exposure will be summarized as a categorical variable classified into <4 weeks, ≥ 4 – <12 weeks, ≥ 12 – <26 weeks, ≥ 26 – <52 weeks, ≥ 52 – <104 weeks, ≥ 104 – <156 weeks, ≥ 156 weeks.

Patients in the randomized set who received any wrong study medications will be identified using the information recorded on the DAR page of the eCRF. If there is a record with reason = dispensing error, then the pack number will be used to identify whether or not the patient received the wrong study drug.

Study compliance will be calculated as the percentage of days with study medication intake (taking into account the duration of the drug interruptions) during the period from first intake to last intake.

Study compliance = $100 \times \text{number of days with study medication intake as per protocol} / (\text{Day of the last treatment} - \text{Day 1} + 1)$.

Compliance will be categorized as <80%, 80% -100%, and summarized by treatment arm and source of patients for each of the bottles separately based on the SAF.

2.4.2 Prior, concomitant and post therapies

Medications started prior to study drug in Study A2315, taken concomitantly in Study A2315, and started following last study drug dose (if applicable) in Study A2315 will be summarized by treatment group in separate tables for the SAF. The medication will be classified into “prior”, “concomitant” based on the start/end dates.

Prior: Any medication with a start date before Day 1 in Study A2315.

Concomitant: Any medication with end date on or after Day 1 or ongoing at the end of trial or missing end date and start date on or before the end of the treatment .

Post: Any medication with start date after the end of treatment, including medications taken in the follow-up period. Medications can be considered both prior and concomitant.

Concomitant therapies will be recorded and summarized separately for asthma related medications / non-drug therapies and other medications. Concomitant asthma-related medications will be summarized by pre-defined category. Concomitant medications not related to asthma will be summarized by pharmacological (ATC) class and preferred term. More than one ATC class per medication is possible and the medication will be reported under all applicable classes.

Patients taking prohibited concomitant medications will be noted in the summary of protocol deviations.

2.5 Analysis of the primary objective

2.5.1 Primary endpoint

Primary endpoints for the study are:

Treatment Period 1:

- Time-to-first treatment emergent adverse events (AEs);
- Time-to-first treatment emergent serious adverse events (SAEs); and
- Time-to-first treatment emergent AE leading to discontinuation from study treatment.

of QAW039 (150 mg once daily and 450 mg once daily), compared with placebo in patients with moderate-to-severe asthma receiving SoC asthma therapy.

Treatment Period 1 and Treatment Period 2 combined:

- Time-to-first treatment emergent adverse events (AEs);
- Time-to-first treatment emergent serious adverse events (SAEs); and
- Time-to-first treatment emergent AE leading to discontinuation from study treatment.

of QAW039 (150 mg once daily and 450 mg once daily), compared with placebo in patients with moderate-to-severe asthma receiving SoC asthma therapy.

As this study has been early terminated, the primary endpoint will be analyzed in the way of combined treatment period 1 and treatment period 2. Treatment emergent AEs are defined as adverse events (including asthma exacerbations), starting on or after the day of the first intake of study drug in this study and until the earlier date out of: date of last intake of study drug +7 days (30 days in the case of a serious AE) and final visit.

Any AEs that started during the study after informed consent and before the time of the first intake of study drug will be classified as a prior AE and not classified as treatment emergent AE. The time-to-first treatment emergent AE is defined as the time to the occurrence of an AE from the treatment start date, and computed as time to AE=AE start date – treatment start date +1 day. As a general rule of censoring, patients who either completed the study or discontinued

treatment prematurely or continued treatment and without the event of interest will be censored at the minimum out of the dates of last medication intake + 30 days, final visit date, and date of death. Time-to-first treatment emergent SAEs and time-to-first treatment emergent AEs leading to discontinuation from study treatment are defined in a similar manner as time-to-first treatment emergent AE.

The definition and rationale for the estimand for the primary endpoint are given in [Table 2-1](#). The statistical strategy to handle each intercurrent event is described in more detail in [Section 2.5.3](#).

Table 2-1 Summary of estimand for the primary endpoint

Population		Justification	

Male or female patients aged 12 years and older with moderate-to-severe asthma on standard-of-care asthma therapy and receive at least one dose of study treatment, including two categories of patients:
 
 • Rollover patients: patients completing a prior Phase 3 study (A2307, A2314, A2316, or A2317) of fevipirant; and • New patients: patients with inadequately controlled asthma who had not previously participated in a study of fevipirant. 		
Fevipirant (QAW039) is a Prostaglandin D2 receptor 2 (DP2) antagonist expected to provide benefit in asthma by impacting major effector cells and soluble factors driving airway inflammation in asthma. Treatment with fevipirant should result in a decrease in these parameters of airway inflammation as well as a clinical improvement in asthma.
	
Variables		Justification	

 • Time-to-first treatment emergent AEs • Time-to-first treatment emergent SAEs and • Time-to-first treatment emergent AE leading to discontinuation from study treatment. 		
The primary endpoints provide safety assessments with respect to the timing of first occurrence of treatment emergent AEs, SAEs, and AEs leading to study treatment discontinuation.
	
Intercurrent event	Description	Strategy to handle event	Justification
Discontinuation of fevipirant for any reason without experiencing a safety outcome as defined in the primary variables	Discontinuation of fevipirant for any reason regardless of relation to fevipirant without experiencing a safety outcome as defined in the primary variables	A hypothetical strategy will be used assuming a continued risk for a first event after study treatment discontinuation as described in Section 2.5.3	
These patients may discontinue therapy in clinical practice. Any fevipirant treatment effect would cease almost instantly after discontinuation of fevipirant, and only SoC effect is expected.
 
The safety outcomes would be no more or less likely to occur after discontinuation of fevipirant.

Discontinuation of placebo for any reason without experiencing a safety outcome as defined in the primary variables	Discontinuation of placebo for any reason without experiencing a safety outcome as defined in the primary variables	A hypothetical strategy will be used assuming a continued risk for a first event after discontinuation of placebo as described in Section 2.5.3	
In clinical practice patients receive SoC without additional treatment and the approach for placebo reflects this.

Summary measures			

Hazard ratios comparing QAW039 450 mg once daily, QAW039 150 mg, once daily, and placebo treatments with regard to primary variables.
			

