3.2 Rationale for study design

Asthma is a chronic condition with medications used in patients over long periods of time; therefore, it is important to assess the safety profile of new therapies (such as QAW039) in this setting (i.e., during long-term treatment) to determine whether the safety profile of the respective therapy is maintained with long-term treatment. The purpose of this study is to provide long-term safety data for QAW039 (150 mg once daily and 450 mg once daily), compared with placebo, when added to GINA steps 3, 4, and 5 SoC asthma therapy (GINA 2016), in adult and adolescent (≥ 12 years) patients with moderate-to-severe asthma.

The 2-treatment period, randomized, multicenter parallel-group, study design supports the assessment of the long-term safety profile of QAW039 as add-on treatment for patients with asthma otherwise treated according to GINA 2016 (steps 3, 4, and 5) guidelines. The study is randomized with a control arm (placebo plus standard of care), because a controlled study provides a better assessment of AE data than an open, uncontrolled study in which there is no ability to compare the AEs on treatment with a known control. Additionally, a control arm helps to reduce any potential bias in reporting of adverse events that would result from an open-label study design. The study duration of 3 years (156 weeks) will provide sufficient time for the assessment of the long-term safety profile of QAW039.

Treatment Period 1 is a 52-week, double-blind treatment period. This treatment period will permit a blinded, controlled evaluation of 52-week safety data. Treatment Period 2 is an optional 104-week, single-blind treatment period which will provide longer-term safety data in a controlled, single-blind fashion. Given the long duration of the study and the inclusion of placebo (in addition to SoC asthma therapy) in Treatment Period 1 and Treatment Period 2, investigators will be permitted to adjust a patient's SoC therapy according to their medical judgment during the study.

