9.4.2 Statistical model, hypothesis, and method of analysis

The time-to-first treatment emergent AE will be considered from the start of Study A2315 only and the clinical study report will be based solely on the data from Study A2315.

The primary variable will be analyzed by a Cox regression model stratified by randomization stratum (but not by region):

- patients on QAW039 150 mg once daily treatment in Studies QAW039A2307 and QAW039A2314,
- patients on QAW039 450 mg once daily treatment in Studies QAW039A2307 and QAW039A2314,
- patients on placebo in Studies QAW039A2307 and QAW039A2314,
- patients on QAW039 150 mg once daily treatment in Studies QAW039A2316 and QAW039A2317,
- patients on placebo in Studies QAW039A2316 and QAW039A2317,
- patients who have not previously participated in a study of QAW039,

and treatment group, severity of asthma (GINA treatment steps 3, 4 and 5), and region as fixed class effects.

Hazard ratios comparing QAW039 450 mg once daily, QAW039 150 mg, once daily, and placebo treatments with regard to time to first treatment emergent AEs and their corresponding 95% profile likelihood confidence intervals will be presented. The other primary variables, treatment emergent SAEs and AEs leading to study treatment discontinuation, will be analyzed in a similar fashion.

The detailed statistical analysis plan will pre-specify how strata would be pooled for analysis purposes, if this is necessary.

The same analyses will be performed based on the Treatment Period 1 data and based on the entirety of the study (Treatment Period 1 and Treatment Period 2 combined). A multiplicity adjustment for these two separate assessments is not foreseen.

Summary statistics for the primary variable

[figure not shown]

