9.4.3 Handling of missing values/censoring/discontinuations

Patients that do not experience a treatment emergent AE prior to study end or the day after treatment discontinuation will be considered censored at the time of study end or the day after the last intake of study drug. For the analysis of the 52-week data from Treatment Period 1, patients without a treatment emergent AE during Treatment Period 1 will be considered censored on the day after their last intake of study drug in Treatment Period 1 or on the day of the completion visit (Visit 299) in Treatment Period 1, if the patient continued into Treatment Period 2.

The primary Cox regression model will implicitly impute the censored data under the assumption of independent censoring (conditional on the baseline covariates). That is, a censored patient is assumed to be no more or less likely to experience an event in any future time interval than other patients in the same stratum that continue to be at risk for a first event and that have the same model covariates. The implied assumption of a continued treatment effect after treatment discontinuation is considered conservative for the purpose of the evaluation of safety outcomes that are assumed to be more likely to occur while active treatment is ongoing. The sensitivity analyses described in [Section 9.4.4](#) will evaluate the impact of these assumptions on the trial conclusions.

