1.2 Study objectives and endpoints

1.2.1 Primary Objective

Treatment Period 1 (52-week treatment period):

In patients with moderate-to-severe asthma receiving SoC asthma therapy, to evaluate the long-term safety of QAW039 (150 mg once daily and 450 mg once daily), compared with placebo, as assessed by:

- treatment emergent adverse events (AEs);
- treatment emergent serious adverse events (SAEs); and
- study treatment discontinuations due to treatment emergent AEs.

Treatment Period 1 and Treatment Period 2 combined:

In patients with moderate-to-severe-asthma receiving SoC asthma therapy, to evaluate the long-term safety of QAW039 (150 mg once daily and 450 mg once daily), compared with placebo, as assessed by:

- treatment emergent AEs
- treatment emergent SAEs; and
- study treatment discontinuations due to treatment emergent AEs.

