While no formal hypothesis testing is foreseen for the primary safety objectives, if both QAW039 doses have a 50% relative hazard increase for treatment emergent events, compared with placebo, then there will be approximately > 99%, 94% and 38% power that the two-sided 95% confidence interval not adjusted for multiplicity for one of the two QAW039 doses would exclude no effect for the primary safety variables of time-to-first treatment emergent AE, time-to-first treatment emergent SAE, and time-to-first treatment emergent AE leading to study treatment discontinuation analyzed across Treatment Period 1 and Treatment 2 combined, respectively. The power was estimated using 10,000 simulations based on 1,570 patients being randomized into the current study. In addition, the sensitivity of the power is further assessed for different scenarios of sample size (1470 patients and 1670 patients). This power will be higher, if more patients are randomized (e.g., due to additional new patients being enrolled) or more patients completing prior Phase 3 studies of QAW039 elect to participate in the current study.

The underlying assumptions for the power simulations were an exponential censoring rate in the placebo group of 0.22 and of 0.16 in the QAW039 treatment groups. The assumptions on the exponential event rate in each treatment group are shown in [Table 3-1](#). These assumptions are based on the, DREAM ([Pavord et al. 2012](#)) and MENSA ([Ortega et al. 2014](#)) trials, as well as a QAW039 Phase 2 study in moderate-to-severe asthma. The detailed power calculations are shown in the [Table 3-2 and Table 3-3](#).

Table 3-1 Assumed placebo event rates for power calculations

Endpoint	Previous study patients were enrolled in or new patients	Assumed exponential event rate (per patient-year)
Rate of AEs	QAW039A2316/ QAW039A2317	3.01

	QAW039A2307/ QAW039A2314	2.86
	New patients	2.86
Rate of SAEs	QAW039A2316/ QAW039A2317	0.07
	QAW039A2307/ QAW039A2314	0.24
	New patients	0.24
Rate of AEs leading to study treatment discontinuation	QAW039A2316/ QAW039A2317	0.03
	QAW039A2307/ QAW039A2314	0.03
	New patients	0.03

Table 3-2 Power (%) for a non-multiplicity adjusted confidence interval to exclude no-difference versus placebo for the primary safety variables

Primary Endpoint	Treatment Period	QAW039 150 mg versus placebo	QAW39 450 mg versus placebo	Both QAW039 150 mg and 450 mg versus placebo	One of the two QAW039 doses versus placebo
Time-to-first AE	1	>99	>99	>99	>99

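### The SAP keeps Treatment Period 1 as a primary objective with its own endpoints, but its visible text plans only a combined-period analysis, so the 52-week comparison has no separate hazard ratio

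*SAP*

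**What the plan says.** **Protocol.** Section 2.1 sets two primary objectives, one for Treatment Period 1 and one for both periods combined. Section 3.2 gives the purpose of the first period: "This treatment period will permit a blinded, controlled evaluation of 52-week safety data". Section 9.4.2 states: "The same analyses will be performed based on the Treatment Period 1 data and based on the entirety of the study". Section 9.4.3 adds a Period 1 rule: "For the analysis of the 52-week data from Treatment Period 1, patients without a treatment emergent AE during Treatment Period 1 will be considered censored". The censoring date is the day after last intake in Period 1, or Visit 299 for patients who go on to Period 2.

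**SAP.** Section 1.2.1 still carries a separate objective headed "Treatment Period 1 (52-week treatment period"). Section 2.5.1 lists three Period 1 endpoints (first AE, first SAE, first AE leading to discontinuation) and the same three for the combined periods. It then says, giving early termination as the reason, that "the primary endpoint will be analyzed in the way of combined treatment period 1 and treatment period 2". Section 2.5.2 specifies one Cox analysis, and 2.5.3 has no week-52 or Visit 299 cut-off. Section 3 still shows Period 1 power rows. The visible bullets of section 4, which list departures from the protocol, do not mention dropping the Period 1 analysis.

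**The concern.** A primary objective and three primary endpoints are stated, but no visible analysis is matched to them. The only reason given is early termination. A Cox model handles short follow-up by censoring, and stopping a study early removes late follow-up before it removes first-year follow-up. Termination therefore weakens the long-term question more than the 52-week one.

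The two hazard ratios answer different questions. Period 1 covers every treated patient over the first year. In the combined analysis, the risk sets after week 52 contain only patients who gave a second consent at Visit 301 and stayed on drug. If the hazard ratio changes over time, or if entry to Period 2 is related to risk, the combined estimate can differ from the 52-week one, and the reader would have no estimate to set beside it.

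**Working it through.** **1. Can the Period 1 analysis be done?** SAP Table 3-2 gives Period 1 power for SAEs at 1,570 patients as 65/65/54/76% (150 mg, 450 mg, both doses, one of the two). I simulated a stratified Cox model with the plan's inputs: 3:3:1 allocation, hazard ratio 1.5, exponential placebo event rates from Table 3-1, exponential censoring at 0.22 per year on placebo and 0.16 on active, a cut at 1 year, and profile-likelihood 95% intervals. Two simplifications were made: two strata, and no region or GINA terms. The number of rollovers from A2316/A2317 is not stated, so 150 to 450 was tried as an assumption.

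- SAE, Period 1: 65.9/65.4/54.7/76.6% with 300 such rollovers and 64.3/65.4/54.5/75.1% with 350. Over the whole assumed range, power per dose is about 62-68%.
- Discontinuation AE, Period 1: 16.4/16.8/9.9/23.4% (stated 16/16/9/22).
- Any AE: above 99%, as stated.

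The plan's Period 1 figures reproduce to within about 2 points. (Combined-period results came out about 1 to 4 points above the stated ones.)

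**2. How much of the combined result comes from after week 52?** With event rate λ and censoring rate c per year, the probability of an observed first event by time t is

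P(t) = λ/(λ+c) × (1 − exp(−(λ+c)t)).

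The share falling after week 52, with follow-up to week 156, is 1 − P(1)/P(3). Active-arm λ is 1.5 times the placebo rate.

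Example, SAE on placebo: λ = 0.24, c = 0.22, λ+c = 0.46. P(1) = 0.24/0.46 × (1 − exp(−0.46)) = 0.192. P(3) = 0.24/0.46 × (1 − exp(−1.38)) = 0.390. Share = 1 − 0.192/0.390 = 51%.

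| Endpoint (placebo rate per year) | Placebo: P(1), P(3), share | Active: P(1), P(3), share |
|---|---|---|
| Any AE (2.86) | 0.886, 0.929, 5% | 0.953, 0.964, 1% |
| Any AE (3.01) | 0.895, 0.932, 4% | 0.957, 0.966, 1% |
| SAE (0.24) | 0.192, 0.390, 51% | 0.281, 0.547, 49% |
| SAE (0.07, A2316/A2317) | 0.061, 0.140, 57% | 0.092, 0.217, 58% |
| Discontinuation AE (0.03) | 0.026, 0.063, 58% | 0.041, 0.101, 60% |

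**3. How far do those shares fall?** The documents give neither actual follow-up nor Period 2 uptake, so these are assumptions.

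- Follow-up capped at 2 years, 1 − P(1)/P(2): SAE 37-43%, discontinuation AE 44-45%.
- Follow-up capped at 18 months, 1 − P(1)/P(1.5): SAE 25-29%, discontinuation AE 29-30%.
- No early stop, but only a fraction q enters Period 2, with share q(P(3)−P(1)) / (P(1)+q(P(3)−P(1))). For q from 0.5 to 0.8: SAE at 0.24, 32-45%; SAE at 0.07, 40-52%; discontinuation AE, 41-54%.

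Termination and optional entry together would lower the shares further.

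**4. Precision of a Period 1 result at the design size.** The 95% interval is the hazard ratio multiplied and divided by the factor below.

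| Endpoint | Period 1 | Combined, to week 156 |
|---|---|---|
| Any AE | 1.17 | 1.17 |
| SAE | 1.41-1.45 | 1.27-1.29 |
| Discontinuation AE | 2.44 | 1.78 |

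**The case against.** **It is a disclosed decision.** SAP 2.5.1 states the combined choice and its reason. That stands: nothing is hidden. What is missing is agreement between that sentence, the objectives and endpoints still listed, and section 4. Some section 4 bullets and parts of SAP section 2 are redacted, so the finding is limited to the visible text.

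**The 52-week question is not wholly unanswered.** A reader might infer that the first primary objective goes unaddressed. The documents do not support that. SAP 2.5.2 plans Kaplan-Meier curves by arm, which show the first year for each endpoint, and for any AE the combined hazard ratio is nearly the Period 1 result. What is absent is a separate Period 1 hazard ratio, mainly for SAEs and discontinuation AEs.

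**Blinding does not separate the periods cleanly.** A reader might infer that the combined estimate mixes sound blinded data with a compromised extension. Investigators and patients, who report the events, stay blinded in both periods (Protocol 3.1). Sponsor blinding during Period 1 is not guaranteed either: Protocol 3.1 and 5.4 allow sponsor personnel to be unblinded at an interim analysis. The documents show no route from sponsor unblinding to biased first-event reporting.

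**The combined model is not an analysis of volunteers.** It starts at first dose in all treated patients. Those who decline Period 2 keep their Period 1 events and time and are then censored. The residual issue is independent censoring, an assumption SAP 2.5.3 states openly.

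**The protocol's Period 1 rule cannot be used unchanged.** It censors on the day after last intake. SAP 2.5.1 widens the treatment-emergent window to 7 days after last intake (30 for SAEs) and censors at up to 30 days. Taking over the old rule would change the event definition as well as the period. This stands and shapes the fix.

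**Conclusion.** The point holds as a mismatch between objective and analysis. The protocol required a Period 1 Cox analysis, the SAP keeps the objective and endpoints, and the visible SAP neither plans that analysis nor lists its removal in section 4. Early termination does not prevent it.

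The consequence depends on the endpoint. It is negligible for any AE, with about 1-5% of first events after week 52. It can matter for SAEs (49-51% at rate 0.24, 57-58% at rate 0.07) and for AEs leading to discontinuation (58-60%). Those shares rest on the plan's assumed rates, follow-up to week 156 and full entry into Period 2, so they are upper figures. The true shares are lower by an amount the documents do not allow one to fix. None of this shows that the combined hazard ratio is biased; it shows that the 52-week estimate was promised and is not visibly planned. The plan should be changed, but the combined analysis remains valid for its own objective.

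**What to change.** For each of the three primary endpoints, also fit the SAP 2.5.2 Cox model to Period 1:

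- Censor patients who continue into Period 2, without an event, at Visit 299.
- For patients who stop drug in Period 1, including those still in Period 1 at termination, keep the SAP 2.5.1 treatment-emergent window (7 days, 30 for SAEs) and the SAP 2.5.1 censoring rule, so that the two hazard ratios share one event definition.
- Report the Period 1 result beside the combined one, and record any remaining departure from Protocol 9.4.2 in SAP section 4.

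If the sponsor still prefers the combined analysis alone, SAP 1.2.1 and 2.5.1 should stop listing Period 1 as separately analysed and section 4 should say so. That removes the inconsistency but leaves the 52-week hazard ratio unreported.

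The cost is three more model runs and tables, with no new data. The Period 1 intervals for SAEs and discontinuation AEs will be wider than the combined ones and should be read as such.
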